5. BACKGROUND*

Frail older adults are at elevated risk for adverse postoperative outcomes. With aging, impairments underlying physical function emerge, such as muscular weakness, decreased lower extremity proprioception/balance, and visual deficits. These impairments limit walking ability which in-turn limits participation in daily life activities. A more sedentary lifestyle ensues leading to further lower extremity weakness which becomes manifest in slow gait speed.⁵ These sedentary individuals also undergo significant loss of endurance/exercise capacity as their bodies becomes less efficient at using oxygen.⁶ This is significant given the stress on the body during surgery. Frail older adults are also at risk for delayed mobilization which can lead to multiple other medical complications. Afilalo et al.¹ found that cardiac surgery patients with slow gait speed, a good single marker of frailty, had more than a threefold increase in morbidity and mortality (odds ratio= 3.05 95% CI 1.23-7.54)

In that study, the authors used gait speed < 0.83 m/s which is a relatively stringent criterion for slow speed. Using a more liberal gait speed criterion (≤ 1.0 m/s), our research group still found a 1.7 fold increased risk (hazard ratio=1.71 95% CI 0.67-4.31) of developing an adverse postoperative course for older adults.⁷

A pure walking intervention (without resistance or other exercise components) can lead to improved physical status in frail older adults but it has not been tested previously in the surgical setting. Investigators have shown that long term care residents (typically frail) can participate and benefit from regular walking.⁸ Similarly, investigators with the COPD Seat study⁹ have

INVESTIGATOR STUDY PLAN - REQUIRED

proposed looking at whether a two-week movement intervention (i.e. essentially a walking program) titrated to step count can improve balance, gait speed, and strength in patients discharged after hospitalization for COPD.

Our proposal will assess the role of a walking intervention in the surgical context assessed over multiple dimensions of physical status-endurance, balance, gait speed, strength, and self-reported function.

The gains we achieve with the walking intervention will pay dividends in terms of clinical endpoints. We hypothesize that a preoperative walking intervention will lead to improvement in physical status by the time of surgery.

Prior studies did not use pedometers and also did not isolate the most vulnerable participants like frail older adults. Gillis et al.² studied 77 patients of varying physical status (i.e. all comers) scheduled in a randomized control trial. In this trial the authors compared a tri-modal intervention administered 4 weeks preoperatively and 8 weeks postoperatively for improving endurance, nutrition, and anxiety compared with a group that received this only postoperatively. At the end of the preoperative phase, patients receiving pre-habilitation walked on average 41.6m more during six minute walk distance (6MWD) testing than controls. However, the rate of postoperative complications did not differ significantly between groups and the cost and convenience of that intervention were unfavorable.

Dronkers et al.⁴ had both clinic-based and home-based exercise components in their preoperative intervention (with multiple trainers enlisted at presumed great cost). As part of their intervention they tracked patients with traditional pedometers. Despite these comprehensive efforts, they did not find any significant differences in endurance or clinical complications. One explanation for the lack of effect may be that the investigators did not use the pedometer for goal setting. Goal setting has proven itself when it comes to pedometers increasing physical activity / number of steps.¹⁰ In addition, neither the Dronkers nor Gillis study isolated frail older adults whose elevated baseline risk provides an increased opportunity for preventing adverse events.

Impact

We target frail older adults. Unlike prior prehabilitation studies, we focus on frail older adults. Working with this group provides a unique opportunity to make big gains in endurance and other aspects of physical status (relative to baseline status). In future work we can assess whether these relative gains translate into significant clinical outcome reduction.

Our intervention is low-cost and convenient. The convenience to patients of a home walking intervention will pay dividends in terms of adherence. Given the low baseline physical status of the patients we are recruiting, walking is the intervention that makes the most sense.

We are goal setting with a modern pedometer. Goal setting with a modern pedometer will

INVESTIGATOR STUDY PLAN - REQUIRED

overcome the shortcomings of the prior studies^{2,4} that either did not use a pedometer or only used it for research staff tracking steps. By having the user pay close attention to the steps being walked, we anticipate they will walk more than other patients not using a pedometer, consistent with the literature.¹⁰

We are collecting more comprehensive physical status data than prior studies. Prior studies collected endurance but other dimensions of physical status are also important to consider. Improvements in balance and strength can lead to better and earlier postoperative mobilization. Similarly, improved function can predict increased independence with activities of daily living reducing the need for skilled nursing.

6. INCLUSION AND EXCLUSION CRITERIA*

Inclusion criteria for screening - We will enroll participants age 50 and older undergoing any abdominal or thoracic surgery.

Inclusion criteria for randomized controlled trial - We will enroll participants age 50 and older undergoing any abdominal or thoracic surgery.

Exclusions for screening – non-adults, prisoners, Non-English language speaker for whom short form consent is not available.

Exclusions for randomized controlled trial - The exclusions we will apply pertain mainly to the measurement of 6MWD – (1) unstable angina or stable angina with minimal exertion or at rest (2) visual impairment such that walking impairs safety (3) fall within previous three months, (4) resting heart rate of more than 120, a systolic blood pressure of more than 180 mm Hg, or a diastolic blood pressure of more than 100 mm Hg (5) patient who does not walk independently (e.g. wheel chair; cane walking is ok)

Individuals who are not yet adults (infants, children, teenagers)

This study excludes anyone who is less than 50 years old; no children will be included in this study.

Pregnant women

Pregnant women will not be included.

Prisoners

Prisoners will not be included in the study.

Non-English language speaking subjects

INVESTIGATOR STUDY PLAN - REQUIRED

Non-English language speaking subjects for which an IRB approved short form is available will be included; patients speaking a language for which the UMass IRB does not have a short form consents available will not be included.

Adults unable to consent (adults lacking capacity)

Adults who are deemed cognitively impaired or unable to consent will be included; given the topic of study and the inclusion/exclusion criteria, it is possible that potential participants with impaired decisional competency will be identified for this study. If substantial cognitive impairment is indicated through the use of the MiniCog test, we will implement consent procedures consistent with those recommended for patients with cognitive impairment. This includes reviewing consent with a legally authorized representative and close monitoring of patients. If patients appear unduly distressed, they will be withdrawn from the study. Please see section # 30. Consent Process for additional details.

*See also section #18.

7. STUDY-WIDE NUMBER OF SUBJECTS*

N/A; this is not a multi-site study.

8. STUDY-WIDE RECRUITMENT METHODS*

N/A; this is not a multi-site study.

9. STUDY TIMELINES*

The overall study timeline is two years from start of recruitment. The first year will focus on preparation (training on frailty measurement, scripting interviews, and testing the questions we ask) and recruitment of study subjects. Individual subjects will be actively involved for 30 minutes during their first appointment (not including time spent in clinic appointment), approximately 15 minutes during the day of their surgery, and potentially approximately ten additional minutes on their day of discharge from the hospital, though patient data collection will continue for up to one year after the day of surgery.

10. STUDY ENDPOINTS*

Aim 1a: Endurance: For endurance, we will measure 6MWD following the American Thoracic Society (ATS) guideline.¹⁵ Briefly, we will establish an unimpeded 20m course within the colorectal surgery office. Studies have varied with the length of course but a multicenter study mentioned in the guideline statement¹⁵ suggested lengths ranging from 20 to 50m did not significantly change patient walking distance results. Every effort will be made to control for variation, including the amount of encouragement provided by project staff member and stopping conditions. We will follow the ATS guideline providing encouragement at one minute intervals.

Patients may stop by leaning against the wall before resuming. At the end of six minutes, we

INVESTIGATOR STUDY PLAN - REQUIRED

will record patient-perceived exertion using the Borg scale. We will also ask the patient for a reason for stopping. Recording the perceived exertion and reason for stopping will allow us to interpret outlier values and other potential variation among patients who otherwise have similar predicted walk distance. Although a research staff member will record the walk distance, we will require that a RN or another more senior clinician be present during the examination to monitor for patient fatigue or angina. Reasons for immediately stopping a 6MWD include the following:(1) chest pain, (2) intolerable dyspnea, (3) leg cramps, (4) staggering, (5) diaphoresis, and (6) pale or ashen appearance. If space is not available, we will conduct the test on a treadmill with guard rails which should provide adequate safety. An RN or another more senior clinician will be present during the examination to monitor for patient fatigue or angina for subjects completing the assessment on a treadmill as well.

Aim 1a: Balance, strength and gait speed: We will follow the short performance physical battery (SPPB) protocol by Guralnik.¹¹ A research staff member will measure the patient's ability to balance in three separate positions: side-by-side stand, semi-tandem stand, and tandem stand. Scores range from 0 for someone unable to balance in any of the positions to 4 for someone able to stand in each position for 10 seconds. Given we have already measured gait speed during the screening process we will move on to patient's ability to perform five chair sit-to-stand maneuvers with scoring based on the time required.

Aim 1a: Self-reported function: We will administer the 12 items of the Veteran Rand (VR-12) in order to measure self-reported function.¹⁶ We will then calculate the summary physical component score (PCS) using a published algorithm.¹⁶ The algorithm norms PCS to range between 0 and 100, with 50 as a mean, and 10 as the standard deviation for the US population.

Aim 1b: Adherence with exercise: We will measure the percentage of days in which the participant meets his/her step count target for intervention patients and activity journals for both groups of patients

Aim 1b: Patient satisfaction: We will design a custom instrument to assess patient satisfaction with our intervention.

Aim 2: Time and cost to recruit 400 frail older adults: We will calculate the time and cost to recruit 400 patients. We will assess time in multiple ways: number of calendar days and number of working clinic days. For cost, we will assign an hourly wage for research staff member and RN efforts and then multiply by the number of hours required to perform recruitment, follow-up telephone calls, and follow-up assessments.

Aim 3: Postoperative outcomes: we may also measure several postoperative outcomes, including:

Change in six-minute walk distance from baseline

The number of steps per day in the hospital

Time to 100 steps at the day of discharge.

Discharge to skilled nursing facility

INVESTIGATOR STUDY PLAN - REQUIRED

Length of stay

Postoperative Recovery (measured via quality of recovery scale, abdominal surgery impact scale)

Thirty-day outcomes including serious complication, readmission, and death

Aim 4: Thirty-day outcomes including serious complication, readmission, and death

Descriptive variables / covariates. We will collect basic demographic information (age, race, and gender), comorbidity, body mass index information, and surgical information including principal CPT code for surgical procedure and anesthesia type. We will also assess exercise self-efficacy using a modified version of the exercise self-efficacy scale.¹ Exercise self-efficacy is the belief that a patient can exercise targeted amounts without additional assistance from others. Assessing for this will allow us to control for baseline difference in the intervention and control patients that might impact on our interpretation of the efficacy of the intervention. The instrument is a simple inventory of items questioning if a patient can accomplish exercise target under various circumstances. A copy of the instrument has been included with the protocol submission.

11. PROCEDURES INVOLVED*

Recruitment and screening phase:

Using HIPAA waiver, we will review the charts of potential patients prior to scheduled visit in the colorectal surgery office. Typically, we will review charts the day before scheduled visits but up to four weeks prior. In terms of the variables we will collect, we are specifically interested in information about age, sex, race, ethnicity, functional status, height, weight, type of surgery, surgeon, and date and time of appointment in colorectal surgery office. These variables will allow us to compare patients who agree to participate with those that decline for the purpose of reporting generalizability in future scholarship originating from this work. The appointment time and provider involved will help with cueing clinic staff members to broach the subject of participation in the research as described further in the next paragraph. We are also reviewing charts for evidence of guardianship or significant cognitive impairment. Specifically, we will look evidence of guardianship established or prior consent documents signed by somebody other than the patient.

Using the information gathered above, we will request clinic staff members (surgeon, surgical resident, nurse practitioner, nurse, or medical assistant) working in the colorectal surgery office to ask if any patient undergoing intestinal surgery would be willing to speak to a research staff member about our research study. For those agreeing, the research staff member will discuss participation in the frailty screening phase of the study through an informed consent process as described further in section 30. The research staff member will also obtain hipaa authorization to collect postoperative outcomes (aim 3) to all adults aged 50 and above scheduled for colectomy or other intestinal surgery not including hemorrhoid surgery. Investigators have previously demonstrated that the Edmonton frailty scale can predict outcomes of surgery including postsurgical complications and length of stay.² For patients scoring 4 or above (out

INVESTIGATOR STUDY PLAN - REQUIRED

of 17) which has been linked with frailty, we will invite to participate in this study to assess preoperative walking as described further below. For those with score of 4 or below, we will not require any further participation apart from the six-month interview. For patients for whom consent can be obtained at the same visit as patient surgical consultation, we will proceed with the baseline assessment as described below. For patients for whom consent cannot be obtained right away or who prefer to come back at another time, we will schedule a follow-up visit within two weeks of initial visit.

Baseline assessment: The RA will record baseline physical status assessments to establish baseline values. We anticipate this will take approximately 30 minutes in addition to the regular office visit. Included in the baseline assessments will be the 6MWD, the SPPB (See attachment), and the Veteran Rand (VR-12) (see attachment).

We will follow the guidelines set in place by the American Thoracic Society (ATS) for administration of the 6MWD. We will utilize safety precautions such as keeping a chair with wheels at the ready nearby at all times for any patient who becomes dizzy or needs to sit for any reason. The baseline 6MWD will be completed in the hallway of the colorectal surgery office at [name]. This is a very low traffic area but we will also do as much as we can to prevent anyone from walking on the course during use. For later assessments administered in the hospital we will set up temporary cones to ensure that no one walks on the course as the patient is walking. Also per the ATS guidelines, the RA will walk the course prior to the patient, so they can ensure that there are no obstructions on the course that may hinder the patient.

We will also follow the ATS guidelines in regards to instructing and encouraging the patient during the walking test. These instructions are stated as follows:

“After the first minute, tell the patient the following (in even tones): “You are doing well. You have 5 minutes to go.” When the timer shows 4 minutes remaining, tell the patient the following: “Keep up the good work. You have 4 minutes to go.” When the timer shows 3 minutes remaining, tell the patient the following: “You are doing well. You are halfway done.” When the timer shows 2 minutes remaining, tell the patient the following: “Keep up the good work. You have only 2 minutes left.” When the timer shows only 1 minute remaining, tell the patient: “You are doing well. You have only 1 minute to go.” Do not use other words of encouragement (or body language to speed up). If the patient stops walking during the test and needs a rest, say this: “You can lean against the wall if you would like; then continue walking whenever you feel able.” Do not stop the timer. If the patient stops before the 6 minutes are up and refuses to continue (or you decide that they should not continue), wheel the chair over for the patient to sit on, discontinue the walk, and note on the worksheet the distance, the time stopped, and the reason for stopping prematurely. When the timer is 15 seconds from completion, say this: “In a moment I’m going to tell you to stop. When I do, just stop right where you are and I will come to you.” When the timer rings (or buzzes), say this: “Stop!” Walk over to the patient. Consider taking the chair if they look exhausted. Mark the spot where they stopped.”

INVESTIGATOR STUDY PLAN - REQUIRED

Randomization: we will randomize patients in a 1:1 fashion into intervention and control groups using a prespecified table generated by our study statistician. More specifically we will use REDCap software to assign a study arm assignment using randomly permuted blocks of sizes 4 and 6.

Intervention patients: intervention patients will receive a walking prescription weekly calls from a study staff member as described below

Walking prescription: A study staff member in consultation with study physician (PI or co-I) will then provide the initial walking prescription based on the participants' baseline performance on the 6MWD following a published example^{12,13} and will focus the participant on walking at a moderate intensity (level of approximately 3 on the modified Borg Perceived Exertional Scale;¹⁴ laminated Borg scales will be distributed to participants).

Participants may walk steps over the course of a day or in one session. The initial walking prescription will also provide instructions to the participant to increase his/her number of steps each week by 10 to 20%.

A research staff member will then orient the participant to the pedometer

Weekly calls: During the interim between the day of consultation until the day of surgery, a study staff member will make weekly calls to each patient. The calls will provide participants an opportunity to report any symptoms which could warrant stopping the walking regimen and/or seeking urgent medical attention. In addition, we will train the study staff member to troubleshoot any problems setting step count targets or other problems with the pedometer. In cases in which the pedometer fails, we will budget to have additional pedometers available to mail to the patient.

Activity log: we will ask participants to log all of their physical activities-date, activity type, number of minutes. We will submit a copy of the activity log to the irb for approval prior to recruiting randomized participants to complete it.

Control subjects: a study staff member will provide general walking advice with typical warnings about when to stop (e.g., chest pain, breathing difficulty, or fall). Control subjects will receive no other intervention. We will also ask control subjects to log their physical activities.

Preoperative assessment: On the day of preoperative testing, which will usually occur three to five weeks after the baseline measurement, a research staff member or other project staff member will collect the pedometer and record the repeat physical status assessments (6MWD and SPPB). On the day of surgery, we may also place a research grade monitor on patients so as to track their steps while in the hospital.

Hospital period assessment: By the day of discharge, we will collect the research grade monitors and repeat our physical status measurements.

INVESTIGATOR STUDY PLAN - REQUIRED

In order to test the above procedures in the randomized individuals, we will enroll up to 15 patients as test patients. All these patients will undergo screening, baseline assessment/interview, follow-up assessment on day of preoperative testing, in-hospital step tracking and Hospital period assessment.

30 day assessment: Approximately 30 days from day of surgery, at office of surgery clinic, we will repeat our physical status measurements

During the 6MWD measurement issued during the baseline assessment, day of surgery, hospital period, and 30-day assessment, a nurse or more senior clinician will be available during the examination to monitor for patient fatigue or angina.

6 month assessment: We will attempt to make contact by phone, mail, or email with enrolled patients no more than five times total (regardless of the method of contact). For patients not picking up the phone, we will leave a voicemail message up to three times following a script that we will forward to the IRB prior to implementation of this procedure. We will make these attempts over 2 months (i.e. months 7 and 8) and not contact patients after 8 months have elapsed from the day of surgery). During our conversation with patients, we will request information about the occurrence of any serious complication since surgery and also will re-administer VR-12. Our prior experience with contacting patients (Pfizer - Anticoagulation Medical Home study) demonstrated the growing difficulties in reaching patients, particularly older vulnerable adults, often who are shifting location between children and rehabilitation facilities making follow-up more challenging. We will use a mailer or post card (depending on availability/prevailing pricing) for the purpose of this correspondence. (See attached)

NSQIP data download

In order to capture information about patient comorbidities and outcomes, study staff will download information already collected on surgical patients at UMass for the purposes of quality control as organized by the National Surgical Quality Improvement Program. Specifically, the study staff member will search for all records relating to the operation. These records will be stored in a password-protected server, same as for the information collected directly from the patient. A programmer assigned to the project will then link data we collected directly with NSQIP using the medical record number and date of surgery. The project programmer/analysts will assemble a limited dataset with no direct personal identifiers to support merger and creation of a common analytic file.

The analytic dataset will be a limited dataset, containing at a minimum dates and a unique artificial Study ID number that is linked through separate coding to the patient's health record number. This linkage coding will be stored separately from the analysis coding. Analyses will be performed using only limited datasets and only aggregate data will be reported.

We will create the interview scripts and data collection forms as one of our first tasks of the study and will upload for approval. We will not commence with any data collection until the tools have been reviewed and approved by the IRB.

INVESTIGATOR STUDY PLAN - REQUIRED

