4. OBJECTIVES*

Surgery is a life-saving procedure for patients with cancer and can enhance quality of life for patients with intractable abdominal or thoracic disease. Although most patients tolerate the procedure well, frail older adults have as much as a threefold increase in the risk of adverse outcomes after surgery.¹ In response to this risk, some investigators^{2,4} have studied preoperative exercise interventions (a.k.a. pre-habilitation).

So far, pre-habilitation studies^{2,4} have shown improvement in endurance but not a reduction in adverse outcomes such as medical complications, discharge to nursing home, or readmission. Potential explanations are that these studies were too small to show a difference but also they did not focus on frail older adults who could benefit most from prehabilitation. A final explanation is that they relied on clinic visits with physical therapists or kinesiologists which can add to the stress and cost of surgery for patients already burdened with appointments in the short preoperative period.

A home walking prescription self-monitored with a modern pedometer (e.g. Fitbit type wristband) provides a convenient and cost-effective method for prehabilitation. Despite the apparent advantages of a home walking program, no one has demonstrated that such a program can reduce the incidence of adverse outcomes or improve physical status assessments such as endurance, balance, gait speed, strength, and self-reported function. If our investigative group establishes that a walking prescription supported by pedometer improves these assessments, we would be in a favorable position to embark on a larger study to demonstrate a reduction in adverse clinical outcomes.

There are other data that would be helpful to collect prior to embarking on the larger study. These include the role of varying duration of the walking regimen. Given the rush to proceed with surgery in anxious patients, it would be important to know how well the intervention works over the range of times available and if there exists a threshold of duration (e.g. 1-2 weeks) below which a walking prescription would have no effect.

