The Project Manager will assist the Principal Investigator and the Co-Investigators in implementing all aspects of the project. Under the direction of Principal Investigator, the Project Manager will be responsible for day-to-day coordination and oversight of the project, including: developing timelines, work allocation, workflow plans, monitoring project progress and task completion, monitoring spending and effort allocation, and managing correspondence and administrative tasks. S/he will monitor/manage ethics and regulatory approvals (IRB, HIPAA/DUA). The Project Manager will attend and plan for all project-related meetings as needed. S/he will work under the direction of the Principal Investigator to assist with all study activities, preparing IRB submissions and reports, and developing study materials such as development of data collection instruments and intervention-related tools. S/he will be responsible for maintaining communications with all parties participating in the project. She will maintain project documentation and will assist in developing and filing required project reports. Project Managers at the Meyers Primary Care Institute all hold graduate level degrees and have vast experience working on healthcare services research projects.

A research staff member will work under the direction of Principal Investigator, Project Manager and Research Manager to assist with all study activities. S/he will assist the PI and other project staff in managing the administrative activities of the project. S/he will prepare materials for team meetings, and will facilitate communication between all project staff through written correspondence, telephone, fax, and email. A research staff member will be trained to formulate walking prescriptions (with oversight from the PI) as well as conduct the 6MWD measurement. A nurse or senior clinician will be available during the time when a research staff member is conducting the 6MWD measurement.

The REDCap Administrator will be the contact with UMass for all REDCap administrative needs throughout the study. As the appointed REDCap administrator for the Meyers Primary Care Institute site, s/he will have access to all study data collected within REDCap.

All study personnel are required to undergo Human Subjects Training and hold a current CITI Human Subjects Training Certificate and will familiarize themselves with the study protocol and IRB documents.

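### One staff role both takes back the arm-identifying pedometer and runs the effort-dependent follow-up tests, and no assessor masking is planned

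*Combined protocol and SAP*

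**What the plan says.** Section 11 (Preoperative assessment) gives two tasks to one role: "a research staff member or other project staff member will collect the pedometer and record the repeat physical status assessments". The assessments named there are the 6MWD and the SPPB. The sentence does not say which task comes first.

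The pedometer belongs to the intervention arm. In section 11 the orientation ("A research staff member will then orient the participant to the pedometer") follows the walking prescription, and for the control arm, after general walking advice, "Control subjects will receive no other intervention" apart from an activity log. Section 10 (Aim 1b) measures adherence as the percentage of days on which the participant "meets his/her step count target for intervention patients and activity journals for both groups of patients". Section 4 gives a wristband as the example of the device.

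Section 23 adds: "A research staff member will be trained to formulate walking prescriptions (with oversight from the PI) as well as conduct the 6MWD measurement". The weekly calls are made by study staff and are described under the intervention arm in section 11.

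On tester influence, section 10 says: "Every effort will be made to control for variation, including the amount of encouragement provided by project staff member and stopping conditions". Section 11 reproduces a minute-by-minute script for the 6MWD. Neither section, nor any other, mentions blinding or masking of assessors.

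**The concern.** Walking distance, balance holds and timed chair stands depend on effort and on how the test is run. A tester who knows the arm can, without intending it, encourage, wait or stop differently. The commitment to control variation from encouragement and stopping sits awkwardly with handing the tester the one object that identifies the arm.

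These are main Aim 1 outcomes. Section 4 makes improvement in them the basis for a larger trial. Section 13 (Interim Analyses) compares average and median change with the minimal clinically important difference after each batch of 10 patients and allows the intervention to be revised on the result. A shift introduced by the tester could affect both decisions. Section 11 describes baseline testing before randomisation, so such a shift would arise only at follow-up. It would pass straight into the change score, and the planned adjustment for baseline would not remove it.

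**Working it through.** The plan states no figure on this point, so there is nothing to reproduce. The check has two parts.

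**1. Can the tester know the arm?** The places side by side:

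- *Device hand-over (section 11, Preoperative assessment).* The role that tests also collects the pedometer. Order unspecified, so nothing prevents collection first.
- *Visible device (section 4).* A wristband may be seen during the test whenever it is collected.
- *Prescription (section 23).* One role is trained both to set prescriptions and to conduct the 6MWD.
- *Orientation and calls (section 11).* Done by research or study staff, the pool from which the tester comes.
- *Patient.* Participants know their own arm and may mention it.
- *Discharge and 30-day repeats (section 11).* The pedometer has gone by then, and the in-hospital monitor is not described as arm-specific. What remains is the tester's earlier involvement.

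So hand-over is one route among several, and the prescription, orientation and calls come weeks before it.

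**2. Would a small shift matter?** This is an illustration only. Assumptions, none of them from the documents: a two-arm z-test on mean change, nominal two-sided alpha 0.05, no true effect, and a systematic between-arm shift b in SD units of the change score. The documents give no SD and no estimate of b. Sample sizes: section 24 gives 200 subjects, and sections 4 and 25 give 400. Assuming that all are randomised 1:1 and analysed, that is 100 or 200 per arm.

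se = sqrt(2/n); type I error = [1 − Φ(1.96 − b/se)] + Φ(−1.96 − b/se)

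- n = 100, b = 0.10: se = 0.1414, b/se = 0.707; 0.105 + 0.004 = 0.109.
- n = 200, b = 0.10: se = 0.1000, b/se = 1.000; 0.1685 + 0.0015 = 0.170.

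| b (SD, assumed) | 100 per arm | 200 per arm |
|---|---|---|
| 0 | 0.050 | 0.050 |
| 0.05 | 0.064 | 0.079 |
| 0.10 | 0.109 | 0.170 |
| 0.15 | 0.186 | 0.323 |
| 0.20 | 0.293 | 0.516 |

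A larger sample makes the error rate worse, because the shift stays the same while the standard error shrinks. The table shows sensitivity. It does not show that any shift will occur.

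**The case against.** The strongest reply is that tester influence on the 6MWD is already restrained. Section 11 fixes the wording and tone at each minute and rules out other encouragement, including by body language. Section 10 lists six reasons for immediate stopping, requires a nurse or more senior clinician to be present, and records perceived exertion and the reason for stopping. This stands, and it narrows the concern for the walk. It does not conceal the arm. The script still leaves the tester a decision to end the walk, and for the SPPB section 10 cites a published protocol without reproducing any script.

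A second reply is that the plan never claims blinding and that this is preparatory work for a larger trial. Both are true. They bear on how much effort is proportionate; they do not make open testing harmless.

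Three stronger readings are tempting, and the documents do not support them:

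- *That the plan has the device collected before testing.* Section 11 joins the two tasks without a sequence, so staff could already test first.
- *That reordering the visit would keep the tester unaware.* It removes the hand-over cue only. Section 23 and the orientation and calls in section 11 leave other routes open.
- *That the bias can be sized in metres.* Setting an assumed 5 to 15 m against the 41.6 m cited in section 5 gives 5/41.6 = 12% to 15/41.6 = 36%, but this only restates the assumption. The 41.6 m also comes from a three-component programme in patients of varying physical status.

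**Conclusion.** The concern holds in a limited form. As written, the plan has the main physical outcomes tested open-label, by a role that handles the arm-identifying device and may have delivered parts of the intervention. The 6MWD script is a partial safeguard, and the gap is clearest for the SPPB. The size of any bias is unknown, and its direction towards the intervention is plausible but not shown. The error rates calculated here rest wholly on assumed shifts and an assumed test. The conclusion rests on reading the control-arm text as meaning that controls have no study pedometer, which sections 10 and 11 support. This is an inexpensive improvement that the plan should adopt. It is not a flaw that invalidates the design.

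**What to change.** In section 11, for the preoperative visit and for the discharge and 30-day repeats, state that:

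1. Where existing staffing allows, the tester is a project staff member who did not set that patient's prescription, give the orientation or make the calls, and who does not look up the allocation. Section 11 already permits another project staff member to test.
2. The 6MWD and SPPB are completed before any pedometer or log is collected.
3. The nurse or clinician whom section 10 already requires at the walk asks every patient, in both arms, to remove wrist devices and not to mention their group. Asking both arms keeps the request itself from revealing the arm. That clinician's safety role is unchanged and needs no masking.
4. The same clinician collects the pedometer and logs in person on the same day, not by post. Section 13 gives the pedometer memory as 30 days, while the visit usually falls three to five weeks (21 to 35 days) after baseline, so delay could lose adherence data for Aim 1b.
5. The form records whether the tester knew the arm.

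The cost is visit-order wording, one form field and minor scheduling. No additional assessor is needed, because item 1 applies only as far as existing staff allow. Section 11 says that the data collection forms are still to be created and approved, so the field can be included then. Some testers will still know the arm; item 5 lets the report say how many.
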